12.3 Reporting Procedures for Serious Adverse Events

All SAEs occurring during the trial must be reported to GW with any other supporting information and recorded in the AE section of the eCRF. Any ongoing SAEs should be followed up until resolution wherever possible. For all deaths, the working diagnosis or cause of death as stated on a death certificate, available autopsy reports and relevant medical reports should be sent to GW promptly.

All SAEs must be recorded in the eCRF within 24 hours of discovery or notification of the event. GW PVD will be automatically notified that an SAE has been recorded. Any additional information required for a case (follow-up or corrections to the original case) will be requested by GW PVD through eCRF queries.

The investigator should continue to document all AEs which occur up to the last formal follow-up observational period (Visit 8). If the investigator subsequently becomes aware of any deaths or a new IMP-related SAE after the last formal follow-up period of the trial, these should still be reported to the GW PVD.

EudraCT Number: 2019-003369-16 Clinical Protocol Global V3, 23Mar2021

Any other problem discovered after Visit 8 that is deemed to be an unexpected safety issue and is likely to have an impact on participants who have taken part in the trial must be treated as an SAE and reported to the GW PVD. Such post-trial SAEs do not need to be recorded on the participant's eCRF if editing rights to the eCRF have been removed due to final trial data lock. GW PVD may request safety follow-up information after the final trial visit in order to investigate a potential safety issue.

Contact details for the GW PVD are provided at the front of the site files for all trial sites.

12.4 Pregnancy

Any participant, or participant's partner, who has become pregnant whilst receiving IMP, or within 90 days of last dose of IMP, must be reported to the GW PVD. Where possible the investigator should provide the outcome of the pregnancy.

All pregnancies must be recorded in the eCRF within 24 hours of becoming aware. GW PVD will be automatically notified that a pregnancy has been recorded. Any additional information required for a case (follow-up or corrections to the original case) will be requested by GW PVD through eCRF queries.

The investigator is not obliged to actively monitor for any pregnancies that commence more than 90 days after the final dose of IMP. However, if the investigator becomes aware of a new pregnancy outside this time limit then they should report it as above. The GW PVD will follow-up for all pregnancy outcomes.

12.5 Causality Assessment

Causality assessment is required for all AEs and SAEs. Causality assessment must only be assigned by the investigator. All cases judged as having a reasonable suspected causal relationship to the IMP must be reported as such. The expression "reasonable causal relationship" is meant to convey in general that there are facts (evidence) or arguments to suggest a causal relationship.

The following question which must be answered by the investigator for all AEs is used to capture the reasonable causal relationship of an event to the IMP:

"In your opinion is there a plausible relationship to the IMP?" The answer is either "yes" or "no".

Events that start before the first dose of IMP (pre-treatment) should be considered as not causally related. Where a pre-treatment event worsens in severity following the first dose of IMP, a new event record should be entered into the eCRF.

Study Code: GWAP19030

EudraCT Number: 2019-003369-16 Clinical Protocol Global V3, 23Mar2021

Considering the explanation given above, investigators are strongly encouraged to express their opinion on what the cause of an AE might be. For individual participants, the investigator is usually in the best position to assess the underlying suspected cause of an AE. For all AEs and especially SAEs, it is important that the investigator assess not only the possible role of the IMP but also other potential contributing factors. Factors for consideration of the underlying cause may include:

- Medical history.
- Lack of efficacy/worsening of treated condition.
- Concomitant or previous treatment.
- Withdrawal of IMP.
- Protocol-related procedure.

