PP Per protocol

PRN Packaging reference number

PVD Pharmacovigilance Department

QTcF QT interval with Fridericia correction

RNA Ribonucleic acid

RTSM Randomization and Trial Supply Management

SAE Serious adverse event
SAP Statistical analysis plan

SCI-PANSS Structured Clinical Interview Positive and Negative Symptoms

Scale

SOC System organ class

SUSAR Suspected unexpected serious adverse reaction

SQLS Schizophrenia Quality of Life Scale

TBL Total bilirubin

TD Tardive dyskinesia

TEAE Treatment-emergent adverse event

THC Δ^9 -tetrahydrocannabinol

TRH Thyrotropin-releasing hormone

ULN Upper limit of normal

US United States

WOCBP Women of childbearing potential

Confidential Page 26 of 104

EudraCT Number: 2019-003369-16 Clinical Protocol Global V3, 23Mar2021

Definition of Terms

Term	Definition
Day 1	The day a participant first receives investigational medicinal product during the treatment period in this trial.
End of trial	Last participant last visit or last contact, whichever occurs last.
Enrolled participant	Any participant who has provided written informed consent to take part in the trial.
International normalized ratio	A calculation made to standardize prothrombin time.
Investigational medicinal product	Term used to describe both investigational active product and reference therapy (placebo).
Investigator	Trial principal investigator or a formally delegated trial physician.
QT interval	A measure of the time between the start of the Q wave and the end of the T wave in the heart's electrical cycle.

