If the severity of an AE fluctuates day-to-day, for example., a headache or constipation, the change in severity should not be recorded each time. Instead, only the worst observed severity should be recorded with AE start and stop dates relating to the overall event duration, regardless of severity.

A severe AE is not the same as an SAE. For example, a participant may have severe vomiting, but the event does not result in any of the SAE criteria above. Therefore, it should not be classed as serious. The severity of an AE will be recorded as 1 of the following:

- Mild: easily tolerated, does not interfere with normal daily activities, does not require intervention.
- Moderate: causes some interference with daily activities; minimal, local or non-invasive intervention indicated.
- Severe: daily activities limited or completely halted; intervention indicated.

E) Causality

Refer to Section 12.5 above.

EudraCT Number: 2019-003369-16 Clinical Protocol Global V3, 23Mar2021

F) Action Taken with Investigational Medicinal Product

This question refers to the action taken with the IMP due to an AE. The action with the IMP must be classed as:

- Dose increased.
- Dose not changed.
- Dose rate reduced.
- Dose reduced.
- Drug interrupted.
- Drug withdrawn.
- Not applicable.
- Unknown.

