13.4 General Considerations

Unless stated otherwise, continuous variables will be summarized showing the number of non-missing values (n), mean, SD, median, minimum, and maximum, and categorical variables will be summarized showing the number and percentage of participants falling in each category. Unless otherwise specified, tables will be summarized by randomized treatment group.

For clinic visit-based endpoints (unless otherwise specified), baseline is defined as the last record or measure collected prior to the first dose of IMP in the treatment period.

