13.6.4.2 Adverse Events

Adverse events will be coded according to the Medical Dictionary for Regulatory Activities dictionary.

A treatment-emergent adverse event (TEAE) is one that started, or worsened in severity or seriousness, following the first dose of IMP.

Descriptive presentations of TEAEs will be given by preferred term and SOC for the safety analysis set. The number of participants reporting at least 1 TEAE will be provided. AEs will be summarized in terms of the number of participants with at least 1 event (N) and the percentage of participants with at least 1 event (%).

The following summaries will be produced as a minimum:

- All-causality TEAEs.
- Treatment-related AEs.
- All-causality TEAEs by maximal severity.
- All-causality serious TEAEs.
- Treatment-related serious TEAEs.
- TEAEs reported as leading to permanent cessation of IMP.
- Fatal TEAEs.

Confidential Page 85 of 104

EudraCT Number: 2019-003369-16 Clinical Protocol Global V3, 23Mar2021

In the presentation of safety data, data from the GWP42003-P dose groups will be presented separately and compared with placebo. This will allow the possibility to explore any effects of the dose of IMP on safety endpoints.

Supportive summaries of ADRs will be presented.

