- h. An ECG will be performed after 5 minutes in a supine position, if possible. The ECGs should be done in triplicate at screening and baseline to ensure that QTcF < 450 msec (males)/ < 470 msec (females). Any subsequent ECG should be done once and should be repeated 2 times in cases where withdrawal criteria are met (QTcF ≥ 500 msec).
- i. To include HIV, hepatitis B, and hepatitis C.
- j. Plasma concentrations of the background antipsychotic medications will be assessed at Visit 1 and predose relative to the administration of IMP at Visit 4 and Visit 7.
 - CBD and its major circulating metabolites will be assessed at Visit 1 and relative to the administration of IMP at Visits 4 and 7. A PK sample will be collected before the participant's morning dose of IMP and within 12 hours (-3/+6 hours) since last IMP dose (Visit 4 and Visit 7). Following collection, the IMP will be administered with a meal of at least 300 kcal to be provided. At Visit 1, only a baseline PK sample will be collected. At Visit 4 and Visit 7, samples to determine concentrations of CBD and its major circulating metabolites will be collected pre- and postdose, relative to IMP, at a timepoint between 2 to 3 hours. Thereafter optional PK sampling may be collected at postdose time points between 4 to 6 hours and 8 to 10 hours.
- k. A drug screen test (urine) will include alcohol, amphetamines (including ecstasy), barbiturates, benzodiazepines, cocaine, methadone, opiates, and THC. THC will be blinded from Visit 3 to the end of the trial.
- 1. Assessment to be conducted prior to dosing of any regular medication prescribed for the management of extrapyramidal side effects (e.g., anticholinergics, beta-blockers etc.).
- m. Every effort should be made to include informant information in the PANSS assessment through administration of the Informant Questionnaire PANSS. If contact with a participant's informant cannot be made within 3-day window from the date of the study visit, either by phone or in person, then the informant interview should not be considered a barrier to visit progression.
- n. IMP is to be taken orally b.i.d., (e.g., morning and evening) preferably within 30 minutes of a meal using the syringe(s) provided. Participants will be asked to return all IMP (used and unused) at each relevant visit. The first dose of IMP at Visit 2 should be taken at the site.

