5.7.2 Adverse Events

All reported AEs will be classified by system organ class (SOC), preferred term and lower level term using Version 24.1 of MedDRA.

Summaries will be presented by treatment group as well as SOC and preferred term.

A treatment period treatment emergent AE (TEAE) is defined as an AE with a start date on or after the first dose of IMP during the treatment period (Day 1), or an AE that was present prior to the first dose of IMP during the treatment period but has increased its intensity during the treatment period.

If an AE has a partial start date and it is unclear from the partial date (or the stop date) whether the AE started prior to or post first dose of IMP then the AE will be considered treatment emergent and if it is unclear which period the event started, it will be assigned to both periods.

An AE will be considered treatment-related if the plausibility relationship to IMP is recorded on the CRF as 'yes'. If the data on plausibility relationship to IMP is missing then the AE will be considered treatment-related.

An AE will be considered leading to permanent discontinuation of IMP if the action taken with IMP is recorded on the CRF as 'trial medication stopped' or the outcome is recorded on the CRF as 'patient died'.

An AE will be considered leading to IMP dose reduction excluding permanent discontinuation if the action taken with IMP is recorded on the CRF as 'dose reduced', 'dose reduced temporarily' or 'trial medication interrupted'.

An AE will be considered leading to temporary IMP dose reduction if the action taken with IMP is recorded on the CRF as 'dose reduced temporarily'.

An AE will be considered leading to permanent IMP dose reduction excluding permanent discontinuation if the action taken with IMP is recorded on the CRF as 'dose reduced'.

An AE will be considered fatal if the outcome is recorded on the CRF as 'patient died'.

For the summary of TEAEs by maximal severity, for each participant, the worst severity recorded by preferred term, SOC and overall will be used for summary purposes. If severity is missing, the worst case (severe) will be assumed.

For summaries by resolution, AEs with an outcome of 'recovered' or 'recovered with sequelae' will be summarized as 'Resolved' and AEs with an outcome of 'continuing', 'patient died' or those with a missing outcome will be summarized as 'Not resolved'.

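### The protocol's new-record rule and TEAE definition start at the first IMP dose (run-in placebo) while the SAP's TEAEs start at Day 1, so the data needed to count worsened run-in AEs may be missing, and the SAP also drops worsening in seriousness.

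*Protocol*

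**What the plan says.** **Recording rules (Protocol).** Section 12.5 reads: "Events that start before the first dose of IMP (pre-treatment) should be considered as not causally related". It continues: "Where a pre-treatment event worsens in severity following the first dose of IMP, a new event record should be entered into the eCRF". The Definition of Terms makes IMP cover placebo as well as active product. Appendix 1, footnote n, places the first dose in the run-in: "The first dose of IMP at Visit 2 should be taken at the site". Section 12.6 D deals with severity that fluctuates from day to day. There, "only the worst observed severity should be recorded with AE start and stop dates relating to the overall event duration".

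**TEAE definitions.** Protocol 13.6.4.2 defines a TEAE as "one that started, or worsened in severity or seriousness, following the first dose of IMP". SAP 5.7.2 has two limbs. The first is a start date on or after the first treatment-period dose (Day 1). The second is an AE "present prior to the first dose of IMP during the treatment period but has increased its intensity during the treatment period". The second limb does not mention seriousness.

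**Onset timing.** The SAP 5.7.2 summary by time of first onset uses AE start date minus the date of the first treatment-period dose, plus 1. Its earliest category is Day 1 to 14.

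**The concern.** In a placebo run-in design, an AE that begins on run-in placebo and worsens once blinded treatment starts is the case for which a worsening limb is needed. That limb can be applied only if the data show that intensity rose after Day 1. A record with a run-in start date and one severity grade does not show this. It also carries one causality answer for both periods.

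If the drug does make existing events worse, such records would be more common in the active arms. Failing to recognise them would then shrink the observed difference from placebo. The two documents also disagree on whether an event that becomes serious, without a change in intensity, is treatment-emergent.

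**Working it through.** The plan has no figure to reproduce, so the check sets the rules side by side and applies them to an example.

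**Step 1: which dose is the anchor?**
- Protocol 12.5 and 13.6.4.2 say first dose of IMP, with no qualifier. With IMP including placebo and the first dose at Visit 2 (Day -14), the literal anchor is the start of the run-in.
- Where the protocol means Day 1 it says so. Section 13.4 has: "baseline is defined as the last record or measure collected prior to the first dose of IMP in the treatment period". Section 13.6.1 uses the same qualifier.
- SAP 5.7.2 uses the first treatment-period dose.
- Hence an AE that starts on Day -14 to Day -1 after the Visit 2 dose and never changes is a TEAE under the protocol's literal wording but not under the SAP.

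**Step 2: follow one event, mild from Day -7 and severe from Day 20.**

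| How it is recorded | Limb 1 (onset on or after Day 1) | Limb 2 (intensity rises in the treatment period) | Onset category |
|---|---|---|---|
| New record opened at worsening | Met, start Day 20 | Not needed | Weeks 3–4 (Day 15 to 28) |
| One record, start Day -7, severity severe | Not met | True in fact, but the record holds no earlier grade and no date of worsening | None, see step 3 |

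Under Protocol 13.6.4.2 the event is a TEAE either way, because it began after the Visit 2 dose.

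**Step 3: the onset day if the single record is flagged anyway.** SAP 5.1.2 numbers days before Day 1 as date minus date of Day 1, so the start is -7. The onset formula gives -7 + 1 = -6. Over the run-in, the result runs from -14 + 1 = -13 to -1 + 1 = 0. None of these values falls in a category, because the first begins at Day 1. The SAP's rule favouring treatment emergence is for partial start dates, so it does not help when the run-in date is complete.

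**Step 4: seriousness.** Take a run-in event of constant intensity that becomes serious after Day 1. Protocol 13.6.4.2 counts it. On its original record it meets neither SAP limb, so it is absent from the serious-TEAE summaries (SAP Appendix 4, Tables 14.3.4.1 and 14.3.4.2). Listing 16.2.7.4 covers serious adverse events generally and would still show it. The new-record rule in 12.5 refers only to severity, so it does not prompt a new record here.

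**Step 5: size.** The documents give no rate of run-in AEs and no rate of worsening, so no count can be derived. For the weight of one record only: 80 randomized at 2:2:1:1 is 80 × 2/6 = 26.7 per active arm. One participant is then 1/27 = 3.7% of an arm, or 1/53 = 1.9% of both active arms together.

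**The case against.** A reader might infer that a worsened run-in AE keeps its run-in start date and drops out of the SAP's TEAEs. The documents do not support that.

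- The second limb of SAP 5.7.2 includes such events by definition.
- Protocol 12.5 requires a new record in one situation and forbids it in none. Protocol 12.1.1 treats worsening of a pre-existing condition after screening as an AE in itself, which permits a new record.
- The single-record rule in 12.6 D is limited to day-to-day fluctuation. A sustained step from mild to severe is outside it, so nothing obliges a site to store that event as one record.
- The term pre-treatment in 12.5 could have been meant as before the treatment period. The protocol separates the two periods, and the SAP has a listing of pre-treatment AEs.
- The case report form that the SAP cites and any completion guide are not among the documents. They may date severity changes.

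These points stand and limit the finding to a gap in the rules; they do not show that events are lost. The ambiguity argument is the weakest, because the protocol adds the treatment-period qualifier elsewhere and omits it here. Permission to open a new record is also not an instruction, so sites may differ.

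A reader might also want a percentage of participants misclassified, or might argue that one record decides the 2% threshold of Table 14.3.2.8. Any percentage would rest on assumed rates. The table title does not settle whether the threshold is per arm (3.7%, reached) or pooled (1.9%, not reached), and a single event of any kind has that weight.

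**Conclusion.** The concern holds in a limited form. The protocol and SAP use different anchors. No section expressly requires the record that the SAP's worsening limb relies on when a run-in AE worsens after Day 1, and for fluctuating events the protocol asks for a record that cannot show the rise. Worsened run-in AEs may therefore go unrecognised or, if flagged on their run-in start date, have no onset category. This rests on the literal reading of first dose of IMP and on the case report form not dating severity changes.

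The omission of seriousness is a plain mismatch between the documents and does not depend on the anchor reading. Its effect is confined to the TEAE tables, since the SAE listing still carries the event. The number of participants affected is unknown. Any bias towards no difference is conditional on the drug worsening existing events.

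**What to change.** **SAP 5.7.2.** Add worsening in seriousness to the second limb. State that the onset date of a worsened event is the date of worsening, so that it falls in an onset category.

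**Before unblinding.** Query each run-in AE that was ongoing at Day 1 for the date of any worsening, any change in seriousness, and causality after that change. The blinded data review meeting in SAP section 4 is a natural point at which to close these queries.

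**Protocol wording.** Anchor 12.5 and 13.6.4.2 to the first dose in the treatment period. Have 12.5 require a new record, with its own start date and causality answer, when an event present before that dose worsens in severity or becomes serious after it. Exempt worsening across that dose from the single-record rule in 12.6 D.

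**Cost.** A few sentences, a limited query list and some extra AE records. Because the study ended early with 80 randomized, the protocol wording serves only future use of the text and cannot alter records already collected. For this trial the SAP edit and the queries are what can still help.

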12.6 Reporting Procedures for All Adverse Events

All AEs (including SAEs) occurring during the trial will be reported on the running logs in the AE section of the eCRF. This includes all events from the time following screening (Visit 1) up to and including the post-trial follow-up visit (Visit 8), whether attributed to IMP or not and observed by the investigator or participant.

The following information will need to be provided for all AEs:

A) Adverse Event (Diagnosis or Syndrome if Known, or Signs and Symptoms)

Where the investigator cannot determine a diagnosis, signs or symptoms should be recorded in the AE section of the eCRF. Once a diagnosis has been determined the AE section of eCRF must be updated to reflect the diagnosis in replacement of the original symptoms. In circumstances where only a provisional diagnosis is possible (working diagnosis), the eCRF must be updated to reflect the provisional diagnosis in replacement of the original symptoms. In some circumstances it may be relevant for the investigator to include the symptoms alongside the diagnosis in the verbatim event description. However, the diagnosis (full or provisional) should be clearly stated, e.g., fever and malaise due to respiratory tract infection.

B) Adverse Event Start Date and Stop Date

The start and stop dates of the event must be provided. All AEs require these fields to be completed in full. Partial dates or missing dates are not normally acceptable and significant effort must be undertaken to obtain any unknown information. If a precise date is not known an estimated date should be provided instead. When a complete date cannot be given, record as much information as possible (i.e., month and year or,

Confidential Page 72 of 104 Clinical Protocol Template (Phase 2–4)

EudraCT Number: 2019-003369-16 Clinical Protocol Global V3, 23Mar2021

in exceptional circumstances, just year). When the actual start date becomes known the eCRF must be updated to replace the previously recorded date.

C) Outcome

The outcome of the event must be recorded accurately and classified as either:

- Fatal.
- Not recovered/Not resolved.
- Recovered/Resolved.
- Recovered/Resolved with sequelae.
- Recovering/Resolving.
- Unknown.

D) Severity

When describing the severity of an AE the terms mild, moderate, or severe should be used (see below). Clinical judgment should be used when determining which severity applies to any AE.

If the severity of an AE fluctuates day-to-day, for example., a headache or constipation, the change in severity should not be recorded each time. Instead, only the worst observed severity should be recorded with AE start and stop dates relating to the overall event duration, regardless of severity.

A severe AE is not the same as an SAE. For example, a participant may have severe vomiting, but the event does not result in any of the SAE criteria above. Therefore, it should not be classed as serious. The severity of an AE will be recorded as 1 of the following:

- Mild: easily tolerated, does not interfere with normal daily activities, does not require intervention.
- Moderate: causes some interference with daily activities; minimal, local or non-invasive intervention indicated.
- Severe: daily activities limited or completely halted; intervention indicated.

E) Causality

Refer to Section 12.5 above.

EudraCT Number: 2019-003369-16 Clinical Protocol Global V3, 23Mar2021

F) Action Taken with Investigational Medicinal Product

This question refers to the action taken with the IMP due to an AE. The action with the IMP must be classed as:

- Dose increased.
- Dose not changed.
- Dose rate reduced.
- Dose reduced.
- Drug interrupted.
- Drug withdrawn.
- Not applicable.
- Unknown.

